At the interim or final efficacy analysis, only the primary efficacy result will be used to determine if the study meets the efficacy criterion. The nominal significance level for the interim or final primary and key secondary efficacy endpoints for a 2-sided at a 0.05 significant level are specified below, calculated using East® 6.4. The calculations are based on 60% of planned sample size, and will be updated based on the actual information fraction at the interim analysis.

	Efficacy Boundary p-value Scale	
	Interim Analysis	Final Analysis
Primary Endpoint	0.0074	0.0477
Key Secondary Endpoint	0.0354	0.0257

Separately, if the primary efficacy criterion is met at the interim analysis, the interim analysis dataset together with overrun data will be used to evaluate the dose-response relationship with the DRAS. If the primary efficacy criterion is not met at the interim analysis and study continues to its completion, dose-response evaluation will be conducted using the end of study data.

If the primary efficacy criterion is not met at the interim analysis, and the blinded sample size re-estimation causes a sample size increase, the nominal significance levels at the end of the study will be recalculated, such that the overall alpha level is not greater than 0.05 for the primary and key secondary analyses together. The calculations will be based on the new increased sample size, the actual information ratio, and the alpha already spent.

It is estimated that the interim analysis will take up to 8 weeks from data cutoff to its completion. If the recruitment rate is high and the remaining 40% planned subjects are projected to be all or nearly all enrolled within those 8 weeks, the interim analysis will be waived with reasons documented. In this case, the end of study analysis will be conducted at the 2-sided significance level of 0.05 with primary and key secondary endpoints tested sequentially. Furthermore, the dose-response relationship will be evaluated.

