If the primary efficacy test is rejected, then the key secondary efficacy endpoint will be tested. This testing procedure strongly protects the overall alpha level. In addition, all other efficacy and safety analyses will be conducted at this time.

At the interim or final efficacy analysis, only the primary efficacy result will be used to determine if the study meets the efficacy criterion. The nominal significance level for the interim or final primary and key secondary efficacy endpoints for a 2-sided at a 0.05 significant level are specified below, calculated using East® 6.4. The calculations are based on 60% of planned sample size, and will be updated based on the actual information fraction at the interim analysis.

	Efficacy Boundary p-value Scale	
	Interim Analysis	Final Analysis
Primary Endpoint	0.0074	0.0477
Key Secondary Endpoint	0.0354	0.0257

If the primary efficacy criterion is not met at the interim analysis, and the blinded sample size re-estimation causes a sample size increase, the nominal significance levels at the end of the study will be recalculated such that the overall alpha level is not greater than 0.05 for the primary and key secondary analyses together. The calculations will be based on the new increased sample size, the actual information ratio, and the alpha already spent.

It is estimated that the interim analysis will take up to 8 weeks from data cutoff to its completion. If the recruitment rate is high and the remaining 40% planned subjects are projected to be all or nearly all enrolled within those 8 weeks, the interim analysis will be waived with reasons documented. In this case, the EOS analysis will be conducted at the 2-sided significance level of 0.05 with primary and key secondary endpoints tested sequentially.

Separately, if the primary efficacy criterion is met at the interim analysis, the interim analysis dataset together with overrun data will be used to evaluate the dose-response relationship with the Dose Response Analysis Set (DRAS). If the primary efficacy criterion is not met at the interim analysis and study continues to its completion, dose-response evaluation will be conducted using the EOS data.

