### **9.8.3 Secondary Efficacy Endpoints**

The primary and key secondary efficacy analyses, and dose-response analysis will be conducted separately, and therefore no multiplicity adjustment will be considered for these objectives together.

Using a pre-specified set of candidate dose-response curves that are selected based on prior knowledge of SPD489 dose-response and assumptions on fixed-doses effects (placebo, SPD489 5, 10, 20, and 30 mg), the dose-response relationship of SPD489 as measured by the change from baseline for ADHD-RS-IV Preschool Version Total Score will be evaluated using the DRAS. The MCP-Mod methodology will be used to identify the optimized dose-response curve and the minimum effective dose (MED).

The assumed family of plausible dose-response curves consists of linear,  $E_{max}$ , and logistic relationships, with appropriate parameters, covering the dose ranges of 0 mg (placebo) to 30 mg of investigational product. When the study completes, regardless at the interim analysis or at end of the study, using all cumulative available data, the dose-response relationship of SPD489 as measured by the change from baseline for ADHD-RS-IV Preschool Version Total Score fitting with a candidate curve will be evaluated.

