2.6 Interim Analysis and Multiplicity Adjustments for Type I Error Control

The study implements a group sequential design with 1 interim analysis. The interim analysis is proposed at approximately 60% of planned subjects, who either complete or discontinue the study.

The interim analysis will be conducted on the interim analysis dataset, which is defined as all data from 60% of initially planned subjects who have either completed or discontinued the study, together with data for subjects who are in the study up to the interim analysis data cut time point. The efficacy, safety, and sensitivity on missing data mechanisms analyses at the interim analysis will primarily be conducted using this dataset.

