2.6.2 Interim Analysis

The Lan-DeMets alpha spending function with O'Brien-Fleming boundary will be used for alpha spending between the interim and end of study analysis for the primary efficacy endpoint. Following evaluations in the stage-wise hierarchical setting ([Glimm et al. 2010](#)), the Lan-DeMets alpha spending function with Pocock boundary will be applied to analyze the key secondary efficacy endpoint.

If the hypothesis for the primary efficacy endpoint is rejected at the interim analysis, then the study will be stopped for efficacy and all ongoing subjects from the study (SPD489-347) will be immediately rolled over to the open-label extension study (Study SPD489-348). In this case, using the same data cut point that contains the same information fractions as the primary efficacy interim analysis, the key secondary efficacy endpoint will be tested, and all safety summaries that the DMC to be needed for their decision will be generated, which will include disposition, demographic and baseline characteristics, main AE and vital signs information. Additionally, the incremental data collected during the interim analysis process, i.e., the overrun, together with the interim analysis dataset will be utilized in sensitivity analyses for efficacy and safety. Otherwise, if the primary efficacy criterion is not met at the interim analysis, then the hypothesis for the key secondary endpoint will not be tested at this time, and the study will continue to its completion, at which time the primary efficacy endpoint will be tested. If the primary efficacy test is rejected, then the key secondary efficacy endpoint will be tested. This testing procedure strongly protects the overall alpha level for the primary and key secondary efficacy analyses. All other efficacy and safety analyses will be conducted at this time as well.

At the interim or final efficacy analysis, only the primary efficacy result will be used to determine if the study meets the efficacy criterion. The nominal significance level for the interim or final primary and key secondary efficacy endpoints for a 2-sided at a 0.05 significant level are specified below, calculated using East® 6.4. The calculations are based on 60% of

planned sample size at the interim analysis, and the significance values may be updated (in a blinded fashion), based on the actual information fraction at the interim analysis.

[figure not shown]
| | Efficacy Boundary p-value Scale | |

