|------------------------|---------------------------------|----------------|
| | Interim Analysis | Final Analysis |
| Primary Endpoint | 0.0074 | 0.0477 |
| Key Secondary Endpoint | 0.0354 | 0.0257 |

In general, the nominal significance level used for the interim analysis will no longer apply for the sensitivity analysis, it should be recalculated. However, if the information fraction increase is limited, for example, if the increase is less than 1%, then the nominal significance levels for the interim analysis can be used as a good approximation ([Proschan et al. 2006](#)) for the sensitivity analyses.

If the primary efficacy criterion is not met at the interim analysis, and the blinded sample size re-estimation causes a sample size increase, then the nominal significance levels at end of the study will be recalculated, such that the overall alpha level is not greater than 0.05 for the primary and key secondary analyses together. The calculations will be based on the new increased sample size, the actual information ratio, and the alpha already spent. The new increased sample size extends the information time scale from interval $[0, 1]$ to a wider one. In order to find the critical value for the completion study analysis, the extended time interval will be converted to the original time scale. The information fractions of the interim analysis can be identified within the new time scale. Applying it along with the increased new sample size, the critical values for the completion study analysis can be calculated. This process will be documented prior to database lock and unblinding.

Separately, if the primary efficacy criterion is met at the interim analysis, the interim analysis dataset together with data for the subjects in the study up to the interim analysis data cut time point will be used to evaluate the dose-response relationship over the DRAS. Otherwise, all cumulative data up to completion of the study will be used.

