10.4.2 Dose-response Relationship Evaluations

When the study completes, regardless at the interim analysis or at end of the study, using the MCP-Mod methodology (Pinheiro et al, 2006) and all cumulative available data, the dose-response relationship of SPD489 as measured by the change from baseline for ADHD-RS-IV Preschool Version Total Score will be evaluated on the DRAS, fitting with an optimized candidate curve to identify the minimum effect dose (MED).

The dose response modelling in MCP-Mod uses a nonlinear least squares routine to fit the data to each of the candidate curve. Each of the dose response shapes in the candidate set will be tested using an appropriate contrast T-statistic. Using of the multivariate t-distribution to determine a critical value for all of the contrast T-statistics controls the overall Type-I error rate. The maximum contrast test statistic will be used to select a dose response curve out of the set of significant curves, if there are any significant curves. If at least 1 of the specified candidate curve is selected, using a 2-sided significance level of 0.05, then for this selection process, dose response for SPD489 is established.

The dose response model will include sex (female vs. male), baseline ADHD subtypes and baseline ADHD-RS total scores as explanatory variables in the dose response analysis. The baseline ADHD-RS score will be a continuous covariate, whereas sex and ADHD subtypes will be factors.

The modeling results of the candidate curves will be tabulated that include T-statistic and corresponding adjusted p-values for each curve. Also parameters estimated for the final dose response relationship curve, and figures showing the dose response relationship will be presented. Fitted significant curves with ADHD-RS total score change from baseline data will be displayed as well.

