17. CHANGES TO ANALYSES SPECIFIED IN PROTOCOL

Not applicable.

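### If the trial stops at the interim, SAP 2.6.2 leaves the overrun out of the dose-response and MED analysis, although the protocol includes it and SAP 10.4.2 implies it

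*SAP*

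**What the plan says.** The sentence at issue closes SAP 2.6.2. After a successful interim, dose-response is evaluated on the interim dataset "together with data for the subjects in the study up to the interim analysis data cut time point". If the trial does not stop, all data up to study completion are used.

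Four other places bear on it:

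- SAP 2.6 defines the interim dataset as the data of the 60% who have finished, "together with data for subjects who are in the study up to the interim analysis data cut time point".
- SAP 2.6.2 defines overrun as "the incremental data collected during the interim analysis process, i.e., the overrun", and uses it for efficacy and safety sensitivity analyses. SAP 11 also adds it to the safety reporting after a stop.
- Protocol 9.5.1 says that after a successful interim "the interim analysis dataset together with overrun data will be used to evaluate the dose-response relationship". The synopsis gives the same rule. Protocol 9.8.3 says the evaluation is done "regardless at the interim analysis or at end of the study, using all cumulative available data", and SAP 10.4.2 likewise uses "all cumulative available data" whether the study ends at the interim or at its planned end.
- SAP 17, which lists departures from the protocol, reads "Not applicable".

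**The concern.** For one secondary objective, in one scenario, the documents prescribe two datasets. The protocol's dataset is larger. SAP 2.6.2 is the operative interim text and gives the smaller one, with no declared departure.

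Two things are at stake. First, the MED and its bootstrap confidence interval (SAP 10.4.3) would rest on fewer subjects than the protocol intends. Second, SAP 15 keeps the DMC and the independent reporting team out of the dose-response work. After an early stop, others will do that work knowing that the primary result is positive. With both rules in writing, either dataset could be defended once the results are known.

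**Working it through.** **Can SAP 2.6.2 be read as including overrun?** Write I for the interim dataset, C for in-study subjects' data up to the cut, and V for overrun.

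- By SAP 2.6, I already contains C.
- By SAP 2.6.2, V is collected while the interim analysis is running, that is, after the cut.
- The dose-response sentence in SAP 2.6.2 asks for I plus C, which equals I. V is absent.
- Protocol 9.5.1 asks for I plus V.

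The SAP names overrun elsewhere when it means it (sensitivity and safety analyses), so the two rules are different.

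**The plan's own figure.** The protocol and SAP state 18 completers per arm for 85% power (maximum difference 13.0, SD 14, two-sided 0.05). I used the four SAP candidate curves scaled to 13 points, optimal contrasts and a simulated multivariate-t critical value of 2.18. With 18 per arm the lowest power over the curves is 85.3%; with 17 it is 83.6%. The stated 18 reproduces.

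**How likely is the scenario?** The interim falls at 0.6 × 195 = 117 finished subjects. With 20% dropout that is 93.6 completers, split 5:5:5:5:6, giving 18 per active arm and 21.6 on placebo.

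- Standard error of the pooled comparison: 14 × √(1/21.6 + 1/54) = 3.56.
- Expected z: 8.4 / 3.56 = 2.36. The boundary for p = 0.0074 is z = 2.68.
- Chance of stopping: Φ(2.36 − 2.68) = Φ(−0.32), or about 37%.

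**Precision.** The standard error of one dose against placebo is 14 × √(1/n_placebo + 1/n_dose). The documents give no overrun size. They allow up to 8 weeks for the interim. If 195 subjects are enrolled over 12 to 24 months (assumption), then 195/24 = 8.1 to 195/12 = 16.3 enter per month. Over 8 weeks (8/4.345 months) that is 15 to 30 subjects. I therefore show 10 and 30 additional randomized subjects, each with 20% dropout.

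| Data used | Placebo / each dose | Standard error |
|---|---|---|
| At the cut (117 × 0.8) | 21.6 / 18.0 | 4.47 |
| Plus 10 randomized (127 × 0.8) | 23.4 / 19.5 | 4.29 |
| Plus 30 randomized (147 × 0.8) | 27.1 / 22.6 | 3.99 |

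The standard error falls by 4% (4.29/4.47 = 0.96) to 11% (3.99/4.47 = 0.89). The MED threshold in SAP 10.4.3 is 5.6 points: 5.6/4.47 = 1.25 standard errors at the cut, and 5.6/3.99 = 1.40 with the larger overrun. The MED comes from a fitted curve that borrows across doses, so these figures are an index of precision, not the MED's own standard error.

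**Detection, given a stop.** The conflict arises only when pooled 10/20/30 mg has already beaten placebo at p < 0.0074. I simulated 600,000 trials with 22/18/18/18/18 completers, SD 14 and the four SAP curves, and kept those that stop.

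- SAP curves as written: at least 99.8% show a significant dose-response at the cut, and overrun adds essentially nothing.
- Maximum effect reduced to 8.4: 98.9-99.9% at the cut, and 97.7-99.5% with about 3 more subjects per arm.

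The small fall with overrun is expected. The cut data were selected for being favourable, and new data pull the estimate back.

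**The case against.** The strongest reply is that this is a drafting slip with little reach. The SAP 2.6.2 wording nearly repeats the interim-dataset definition, and every other relevant place points towards including overrun. Only one secondary objective is touched, and only after an early stop. The cut still delivers the 18 completers per active arm that the plan asks for. All of that stands, and it makes the point small. It does not say which text an analyst should follow, and the SAP text is the one that departs from the protocol.

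Three stronger readings are tempting, and the documents do not support them:

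- *Dose-response power is lost.* Ignoring the stopping rule, the lowest power over the curves (scaled to 13 points) is 88.4% at the cut, and 90.8% or 94.4% with 10 or 30 more randomized subjects. A reader might take that gap as the harm. It averages over trials that do not stop, where the conflict does not arise. Given a stop, detection is near certain with either dataset. For the same reason, one minus unconditional power is not the chance of having no MED. SAP 10.4.3 and 10.4.4 also allow an MED to be missing despite significance, and provide fallbacks.
- *Collected data are discarded.* They are left out of the dose-response and MED analysis only, and remain in the sensitivity and safety analyses.
- *The overrun could be very large.* Accrual fast enough to add many subjects per arm within 8 weeks would also enrol nearly all the remaining 40%, and SAP 2.6.1 would then waive the interim.

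Note too that SAP 10.4.2 does not use the word overrun. It implies it; only the protocol names it for this analysis.

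**Conclusion.** The inconsistency holds, both between protocol and SAP and within the SAP. Its statistical cost is a standard error for one dose against placebo of about 4.5 instead of roughly 4.0 to 4.3, with a correspondingly less precise fitted curve, MED and bootstrap interval. Its procedural cost is an open choice of dataset after unblinding; nothing in the documents suggests that such a choice is intended.

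It matters only if the trial stops early, about 37% likely under the planning assumptions. The precision figures assume SD 14, 20% dropout and 10 to 30 additional randomized subjects. They use completers as a stand-in for the Dose Response Analysis Set. That set also admits anyone with one valid score on the target dose, so actual counts will differ. The conditional detection figures use a completer-based test, not the repeated-measures model.

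**What to change.** In the last paragraph of SAP 2.6.2, replace the words quoted from it with *together with the overrun data*. This matches Protocol 9.5.1 and agrees with SAP 10.4.2. Make the change before unblinding. If the exclusion is in fact intended, it has to be declared and justified in SAP 17, and SAP 10.4.2 aligned with it; the rest of the text suggests that it is not.

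The cost is one phrase. Sample size, alpha spending, and the primary and key secondary analyses do not change.

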2.7 Decision Tree of Efficacy Analyses

Note: α_{11} and α_{21} are based on Lan-DeMets alpha spending function with O'Brien-Fleming Boundary

α_{12} and α_{22} are based on Lan-DeMets alpha spending function with Pocock Boundary

*: efficacy boundaries (p-value scale) may be updated based on actual information fraction at the IA

**: will be adjusted based on alpha-spending at IA and the actual sample size at EOS

3. OBJECTIVES

3.1 Primary Objective

The primary objective is to evaluate the efficacy of SPD489 compared to placebo in preschool children (4-5 years of age inclusive at the time of consent) with ADHD. The primary measure of efficacy will be the clinician-administered ADHD Rating Scale Preschool Version (ADHD-RS-IV Preschool Version) Total Score.

3.2 Secondary Objectives

- **Key Secondary:** To evaluate the efficacy of SPD489 compared to placebo, using the global clinical measure of improvement, the Clinical Global Impression – Global Improvement (CGI-I) scale.
- **Secondary:**
 - To evaluate dose-response relationship in preschool children with ADHD, using the ADHD-RS Preschool Version Total Score.
 - To evaluate the safety and tolerability of SHP489 based on the occurrence of TEAEs, specific evaluation of vital signs (systolic and diastolic blood pressure and pulse), height, weight, and body mass index (BMI), clinical laboratory evaluations and electrocardiogram (ECG) results, sleep assessment, and the Columbia Suicide Rating Scale (C-SSRS).

4. SUBJECT POPULATION SETS

The following subject sets are applicable to this study.

4.1 Screened Set

The Screened Set will consist of all subjects who have signed informed consent.

4.2 Randomized Set

The Randomized Set will consist of all subjects in the Screened Set for whom a randomization number has been assigned.

4.3 Safety Analysis Set

The Safety Analysis Set will consist of all Randomized Set who have taken at least 1 dose of investigational product.

4.4 Full Analysis Set

The Full Analysis Set (FAS) will consist of all subjects in the Safety Analysis Set who have at least 1 post-dose ADHD-RS-IV-Preschool Version Total Score assessment.

4.5 Dose-response Analysis Set

The Dose Response Analysis Set (DRAS) will consist of all subjects in the Safety Analysis Set who have at least 1 valid primary efficacy measurement (ADHD-RS- IV Preschool Version Total Score) on the randomized target dose level of the investigational product.

The above analysis sets will be utilized for both the interim and the end of study analyses.

Subjects are randomized at baseline (Visit 0) in a 5:5:5:5:6 ratio to SPD489 5, 10, 20, 30 mg or placebo group. If not stated otherwise, each dose strength and pooled doses (10, 20, 30 mg pooled together) will be used for reporting the study variables, as below.

| Parameter | Placebo | SPD489 | | | | |
|--------------------------|---------|--------|------|------|------|----------------------------|
| | | 5mg | 10mg | 20mg | 30mg | Pooled 10, 20, 30 mg |
| Baseline Characteristics | ✓ | ✓ | ✓ | ✓ | ✓ | ✓ |
| Primary Efficacy | ✓ | | | | | ✓ |
| Key Secondary Efficacy | ✓ | | | | | ✓ |
| All Other Efficacy | ✓ | | | | | ✓ |

| Parameter | Placebo | SPD489 | | | | |
|----------------------------|---------|--------|------|------|------|----------------------------|
| | | 5mg | 10mg | 20mg | 30mg | Pooled 10, 20, 30 mg |
| Dose-response Relationship | ✓ | ✓ | ✓ | ✓ | ✓ | ✓ |
| Safety Reporting | ✓ | ✓ | ✓ | ✓ | ✓ | ✓ |

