#### **Secondary Efficacy Endpoint**

A secondary efficacy endpoint is the dose response relationship of SHP489 for randomized fixed-dose strength (placebo, SHP489 5, 10, 20, and 30 mg), as measured by the change from baseline for ADHD-RS Preschool Version Total Score at study stop (at interim analysis or end of study).

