### **6.2.3 Dosing**

Dosing should begin at approximately 7:00AM ( $\pm 2$  hours) on the morning after the baseline visit (Visit 0). Subjects will be instructed to take 1 capsule daily in the morning throughout the study, at approximately the same time each day. The same parent/LAR should be available daily to dispense the dose of investigational product for the study duration.

SPD489 may be administered in one of the following ways:

- Swallow SPD489 capsule whole, or
- Open capsule, empty and mix the entire contents with yogurt, water, or orange juice.

The contents should be mixed until completely dispersed. The subject must ingest the entire amount of the mixture immediately within 3 minutes. The subject should not take anything less than one capsule per day and a single capsule cannot be split. The empty gelatinous capsule should be discarded into a trash receptacle by the parent/LAR.

Subjects will begin dosing with the lowest strength of SPD489 (5 mg) and will be titrated until the randomly assigned fixed-dose is reached.

Once subjects reach the fixed-dose level, this dose will be maintained until the end of the study.

No dose reductions are permitted during the study. Subjects who are unable to tolerate investigational product will be discontinued.

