#### **7.1.2.2 Dose-maintenance Period (Visits 4 to 6)**

Following titration to the randomly assigned fixed-dose strength of SPD489/Placebo, subjects will continue daily morning treatment for an additional 3 weeks.

Throughout the Dose-maintenance Period, subjects may attend the clinic for unscheduled visits to address any medical needs that arise between scheduled visits.

[Table 1](#) outlines the procedures to be completed at each visit during the Dose-maintenance Period. Additional clarification on the procedures to be performed during the Dose-maintenance Period is provided below:

- Scales are to be completed by the same rater with input from the same parent/LAR whenever possible
- At each visit during the Dose-maintenance Period, subjects must return any empty or unused bottles to permit drug accountability and compliance to be assessed.
- Subjects will be dispensed a 10-count bottle of investigational product to cover them until their next regularly scheduled visit. Subjects will be instructed to take 1 capsule each day. Dosing will begin the morning following each visit.
- The C-SSRS “Since Last Visit” Version of the Pediatric/Cognitively Impaired Version should be completed during the Dose Maintenance Period.
- After 5 minutes rest, blood pressure and pulse will be collected 3 times (with at least 2 minutes in between each collection) during the visit. The average of each set of 3 measurements will be used to determine continued participation in the study (see [Section 4.4.1](#)).

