### 7.1.2.3 End-of-Study Visit (Visit 6/Early Termination)

All randomized subjects who complete the study or discontinue early will complete Visit 6/early termination (ET).

[Table 1](#) lists the procedures to be completed at Visit 6/ET and should serve as the primary point of reference regarding visit-specific study procedures.

Further clarification on the procedures performed during Visit 6/ET is provided below:

- Unused investigational product and empty containers will be collected to calculate medication compliance.
- After 5 minutes rest, blood pressure and pulse will be collected 3 times (with at least 2 minutes in between each collection) during the visit. The average of each set of 3 measurements will be used to determine continued participation in the study (see [Section 4.4.1](#)).

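### The dose-response analysis names no visit; read as each child's last on-target score, it drops more early leavers from the higher-dose arms and can favour high doses when the drug has no effect

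*SAP*

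**What the plan says.** **Who is analysed.** SAP 4.5 (and Protocol 9.7) requires "at least 1 valid primary efficacy measurement (ADHD-RS- IV Preschool Version Total Score) on the randomized target dose level". Completion is not required.

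**Which response.** The protocol synopsis describes the dose-response endpoint "as measured by the change from baseline for ADHD-RS Preschool Version Total Score at study stop (at interim analysis or end of study"). SAP 10.4.2 uses MCP-Mod "and all cumulative available data, the dose-response relationship of SPD489 as measured by the change from baseline". Study stop is an event for the whole trial and does not identify a child's visit. Visit 6 (Week 6) is named for the primary and key secondary endpoints (SAP 10.1 and 10.3), but not in the MCP-Mod text (SAP 10.4.1 to 10.4.3).

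**When target dose is reached.** Protocol 6.2.3: "Subjects will begin dosing with the lowest strength of SPD489 (5 mg) and will be titrated until the randomly assigned fixed-dose is reached". Protocol 7.1.2.2: "Following titration to the randomly assigned fixed-dose strength of SPD489/Placebo, subjects will continue daily morning treatment for an additional 3 weeks". The text gives no step timing and does not say when a placebo child counts as on target.

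**Early leavers.** Protocol 7.1.2.3: "All randomized subjects who complete the study or discontinue early will complete Visit 6/early termination (ET"). SAP 10 discards efficacy scores taken more than 3 days after the last dose.

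**After an interim stop.** Protocol 9.5.1, like the synopsis, says "the interim analysis dataset together with overrun data will be used to evaluate the dose-response relationship with the Dose Response Analysis Set (DRAS"). SAP 2.6.2 instead takes the interim dataset "together with data for the subjects in the study up to the interim analysis data cut time point will be used to evaluate" the relationship. SAP 17 lists no changes from the protocol.

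**The concern.** Reaching the target dose happens after randomisation, and it takes longer the higher the assigned dose. A set defined by it is therefore not a like-for-like comparison of randomised arms unless the visit is fixed. MCP-Mod as described in SAP 10.4.2 is a least-squares fit to change scores, and no rule selects which of a child's scores is used. The wording permits the last on-target score.

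Under that reading two things happen. A child who leaves in the first weeks stays in the 5 mg arm, and in placebo if placebo is on target at once, but is excluded from the 30 mg arm. The scores that remain also come on average from later weeks in the higher-dose arms. If symptoms improve over time without drug, or if poor responders leave more often, both effects make higher doses look better. Dose response is a stated secondary objective, and the same fitted curve supplies the MED.

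**Working it through.** **1. The plan's own figure.** Inputs from SAP 2.5 and 10.4.1: SD 14, maximum difference 13.0, two-sided 0.05, five equal arms, four candidate curves. With optimal contrasts and the multivariate-t critical value, 18 completers per arm give a lowest power of 85.5% over the four shapes (mean 89.9%), so the stated 85% reproduces. For dropout, 18/(1 - 0.20) = 22.5, so 23 against the stated 24. At the planned 36/30/30/30/30 completers power is 97% to over 99%. Sample size is not the difficulty.

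**2. Assumptions not in the documents.** One strength per weekly visit, so the first on-target score is at Visit 1, 2, 3 or 4 for 5, 10, 20 or 30 mg. Placebo is on target from Visit 1. Placebo change is -3, -5, -7, -8.5, -9.5, -10 at Visits 1 to 6; SD 14; within-child correlation 0.6. Dropout occurs after Visits 1 to 5 and totals 20% in every arm.

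**3. Exclusions under random dropout.** The constant hazard per visit is h = 1 - 0.8^(1/5) = 0.0436. A child is excluded if he or she leaves before the first on-target visit f, with probability 1 - (1 - h)^(f-1).

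| Arm | f | Excluded | Mean week of last on-target score |
|---|---|---|---|
| Placebo, 5 mg | 1 | 0% | 5.38 |
| 10 mg | 2 | 4.4% | 5.58 |
| 20 mg | 3 | 8.5% | 5.75 |
| 30 mg | 4 | 12.5% | 5.87 |

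**4. False difference under random dropout.** The chances of leaving after Visits 1 to 5 are 0.0436, 0.0417, 0.0399, 0.0382 and 0.0365; 0.80 complete.
- Placebo mean: -(3 x 0.0436 + 5 x 0.0417 + 7 x 0.0399 + 8.5 x 0.0382 + 9.5 x 0.0365 + 10 x 0.80) = -9.29.
- 30 mg mean with no drug effect: -(8.5 x 0.0382 + 9.5 x 0.0365 + 10 x 0.80)/0.8747 = -9.91.
- Gap: about 0.6 points in favour of 30 mg.

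**5. Rejection rate with no drug effect.** Simulation used 45/38/38/37/37 children, the four SAP shapes and a two-sided critical value of 2.16. For informative dropout the hazard is multiplied by exp(kz - k²/2), where z is the current residual in SD units. The main runs used 10,000 trials per scenario, Monte Carlo SE 0.2 to 0.35 percentage points; smaller repeat runs agreed within simulation error.

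| Dropout (hazard ratio per SD worse) | Last on-target score | False 30 mg advantage |
|---|---|---|
| Random (k = 0) | 5.8% | 0.7 |
| Slight (k = 0.2, x1.2) | 6.1% | 1.0 |
| Moderate (k = 0.4, x1.5) | 7.2% | 1.4 |
| Marked (k = 0.8, x2.2) | 10.8% | 2.1 |

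If early-termination scores fall outside the 3-day rule, the rates are 5.6% (random), 6.7% (moderate) and 7.4% (marked). Week 6 only, or a common window from Visit 4, gives 5.0 to 5.5% with no gap. Week 6 estimates from a five-arm MMRM give 4.5 to 4.8% with no gap (4,000 trials).

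**6. MED at the 5.6-point threshold, taken as a difference from placebo.** True values: the Emax curve gives 19.5d/(15 + d) = 5.6, so d = 84/13.9 = 6.0 mg; the linear curve gives 5.6/0.4 = 14.0 mg. Median estimates for random/moderate/marked dropout, with placebo counted as dose 0 throughout:
- Emax: 6.4/6.5/6.2 mg, against 6.5 to 6.7 with a common visit or the MMRM.
- Linear: 12.0/11.5/11.0 mg, against 12.2 to 12.7.

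With Week 6 scores and random dropout, the central 95% of MED estimates is 0.8 to 17.6 mg (Emax) and 3.6 to 21.6 mg (linear). The shifts are small beside that spread.

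**7. Overrun.** SAP 2.6 already defines the interim dataset as including children still in the study up to the data cut. The SAP 2.6.2 wording therefore adds nothing after the cut, whereas the protocol adds overrun. SAP 10.4.2, by calling for all cumulative data, could be read either way.

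**The case against.** The sample-size text counts completers, and every completer has a Week 6 score, so a Week 6 analysis may be what was meant. In the model above 80 to 91% of analysed scores are at Week 6 in any case (0.80/1 to 0.80/0.8747). The analysis is outside the alpha hierarchy, and SAP 10.4.4 plans an arm-by-arm MMRM on a model like the primary one. With random dropout the Type I effect is negligible. The 10-11% rate needs strongly informative dropout and usable early-termination scores. If better responders leave markedly more often, the rate is 5.8% and the false difference reverses, by 0.7 points. Titration timing is assumed, and the flow chart and decision tree, not shown in the text available, may settle some of it.

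Most of this stands and limits the size of the point. It does not close the gap: the completer wording is a planning assumption while the DRAS admits non-completers, and the arm-by-arm MMRM does not feed the MED.

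A reader might infer that the MED depends heavily on the unstated placebo rule. With placebo on target only from Visit 4 and 5 mg from Visit 1, the Emax median does rise to 7.6/8.9/9.3 mg. No passage supports that mixture. The only hint of a late placebo start, in Protocol 7.1.2.2, speaks of SPD489 and placebo together. Applied to every arm it is simply a common window from Visit 4, which causes no problem.

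**Conclusion.** The concern holds as a specification gap with a conditional consequence. The plan sets an inclusion rule that depends on the arm and names no visit. Under the last-score reading, the assumed weekly steps and time trend, 20% dropout and placebo on target from the start, the 5% test runs at about 5-6%, 7-8% or 10-11% as dropout goes from random to markedly informative (about 7% in the marked case if early-termination scores are discarded). The false 30 mg advantage is about 0.6, 1.4 or 2.1 points.

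The MED effect is secondary. Nor should a reader infer that a common visit makes the MED unbiased: with the linear curve true the median is still 12.2 to 12.7 mg against 14.0, a bias of the estimator that visit choice does not remove. Nothing here touches the primary or key secondary analysis, which are tied to Week 6. Separately, and without any simulation, the protocol and SAP conflict on overrun data in the dose-response analysis after an interim stop.

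**What to change.** 1. In the synopsis and SAP 10.4.2, define the dose-response variable as the Week 6 (Visit 6) change from baseline in all five arms by randomised dose.
2. Preferably fit a five-arm MMRM with the planned covariates (baseline score, sex, ADHD subtype) and pass its Week 6 estimates and their covariance matrix to MCP-Mod, so that children still ongoing at an interim stop contribute.
3. If the DRAS is kept, define membership and the analysed score by one visit window common to every arm, placebo included. This is the smaller change and also keeps the test near 5%.
4. Reconcile Protocol 9.5.1 and SAP 2.6.2 on overrun, and record any departure in SAP 17.

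**Cost.** Wording and modest programming. Week 6 scores alone lose about 20% of children at study end. At an interim stop with 117 finished and 33 ongoing they lose (0.20 x 117 + 33)/150 = 38%. The figure of 33 assumes that ongoing children count in the remaining 40% under the waiver rule: 8r < 78 - 6r gives r < 5.6 per week, over 6 weeks. Simulated power there is 83% (linear) and 88% (Emax), against 90% and 94% with the MMRM. The MMRM relies on missing at random.
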